## 6.13 COLPOSCOPY, PAP SMEARS AND HPV TESTING

Cervical colposcopy will be performed at Day 0 and at Week 96 for all subjects. Photographs of the cervix should be obtained if lesions are identified.

Pap smears will be obtained using ThinPrep® test kits at Day 0, Weeks 12, 48 and 96, and read in a central laboratory. HPV PCR will be performed on the ThinPrep® specimen. At each of these visits, menstrual cycle status & recent gynecologic history will be collected. If the Pap smear result suggests progression to cancer the Investigator may schedule an ad hoc visit to perform a colposcopy and possible biopsy if clinically indicated.

The subject will be requested to abstain from sexual activity and refrain from use of douching or vaginal lubricants/medication for a period of 24 hours prior to collection of ThinPrep® samples to eliminate potential interference with the results of HPV testing.

## 6.14 VULVOSCOPY, PHOTOGRAPHS, AND BIOPSIES

Eligible subjects are enrolled in the study based on the diagnosis of vulvar HSIL confirmed by the PAC. Subjects will undergo vulvoscopy to identify the lesion(s). Interval vulvoscopies will be performed at Day 0, Weeks 4, 12, 27, 48, 74 and 96. Vulvoscopic visualization of a normal appearing vulva is insufficient evidence to confirm disease regression. An additional visit may be scheduled to perform vulvoscopy if worsening of disease is suspected.

Digital photographs of the vulva will be captured after application of acetic acid to document the clinical findings. If a biopsy or surgical excision is performed, images of the vulva should be collected before and after the procedure. Each site will be instructed on 1) the technique for capturing the proper images using a standard approach, and 2) the process for uploading the images to a secure server.

In the case of multifocal disease, the two lesions that potentially contain the most advanced disease as judged by the Investigator and which is of adequate size to ensure that a visible lesion remains after punch biopsy should be chosen for vulvar biopsy and documented using photography.

Biopsies should not be performed at any visit other than at entry (screening), Week 48, Week 74 or Week 96 unless the PI suspects disease progression. All biopsy samples must be sent to the PAC for review. Investigator guidelines for managing the findings of

unscheduled biopsies for suspected disease progression are described in [Table 7](#). Consult the Medical Monitor for any planned departures from these guidelines.

**Table 7: Guidelines for Managing Findings of Vulvar Biopsies for Suspected Disease Progression**

Vulvar Biopsy Results	Action
Vulvar HSIL	May continue study treatment/EP and visits according to protocol schedule of events
Microinvasive or Invasive Carcinoma	Discontinue study treatment/EP and proceed with excisional therapy; continue safety follow-up.

Subject safety is paramount in this study. Therefore, if at any time the Investigator suspects disease progression and the standard of medical care would be to perform an unscheduled biopsy or excision, then his or her medical judgment should prevail over the Schedule of Events on [Table 1](#). Histologic samples and photographic documentation should be obtained for these cases.

#### 6.15 CONCOMITANT MEDICATIONS/TREATMENTS

All medications (prescription and nonprescription) taken within 8 weeks prior to screening biopsy date of eligible subjects must be recorded on the CRF. Actual or estimated start and stop dates must be provided. Medical procedures performed within 8 weeks prior to screening biopsy date of eligible subjects that do not affect subject's eligibility for participation and during the study (including over the counter or herbal), will be recorded on the CRFs. This information will be obtained from the subject and abstracted from any available medical records. The indication for the medication, dose, and dose regimen will be documented. Medication that is considered necessary for the subject's safety and well-being may be given per Investigator discretion and recorded in the appropriate sections of the CRF.

#### 6.16 RESTRICTIONS

The following medications and treatments are prohibited:

- Previous treatment with imiquimod for vulvar HSIL within 4 weeks prior to screening
- Long term use ( $\geq 7$  days) of oral or parenteral glucocorticoids at a dose of  $\geq 20$  mg/day of prednisone equivalent (use of inhaled, nasal, otic and ophthalmic corticosteroids are allowed)
- Disease modifying doses of anti-rheumatic drugs (e.g., azathioprine, cyclophosphamide, cyclosporine, methotrexate), and biologic disease modifying drugs such as TNF- $\alpha$  inhibitors (e.g. infliximab, adalimumab or etanercept) at screening and throughout the study
- Administration of any non-study related, non-live vaccine within 2 weeks of any study treatment or within 4 weeks of any study treatment for any non-study related live vaccine
- Blood thinners/Anticoagulants within 2 weeks of any study treatment

### 6.16.1 OTHER RESTRICTIONS

Subjects should not use alcohol or drugs that would interfere with study requirements during the course of the study and should report ALL medications/drugs taken to the Investigator and/or other study personnel.

Subjects should refrain from becoming pregnant until 6 months following the last dose of investigational product by using appropriate contraceptive measures (See Inclusion Criteria, [Section 4.1](#)). Lapses in contraceptive use should be reported to Investigator and/or other study personnel.

Subject should abstain from sexual activity and refrain from use of douching or vaginal lubricants/medication for a period of 24 hours prior to collection of ThinPrep® samples.

## 7. EVALUATION OF SAFETY AND MANAGEMENT OF TOXICITY

### 7.1 SAFETY PARAMETERS

#### 7.1.1 ADVERSE EVENTS

An adverse event (AE) is defined as any unfavorable and unintended change in the structure, function, or chemistry of the body, or worsening of a pre-existing condition, temporally associated with the use of a product whether or not considered related to the use of the product. In this study, such changes will be monitored, classified, and summarized, as Clinical or Laboratory AEs. Medical condition/diseases present before starting the investigational drug will be considered adverse events only if they worsen after starting study treatment. Throughout the course of the study, all solicited and unsolicited AEs will be monitored and reported on an AE CRF, including the event's seriousness, severity, action taken, and relationship to investigational product(s). AEs should be followed until resolution or stable and the outcome will be documented on the appropriate CRF. All AEs should be recorded in standard medical terminology rather than the subject's own words.

AEs include the following:

- Pre- or post-treatment complications that occur as a result of protocol mandated procedure during or after screening (before the administration of study drug).
- Any pre-existing condition that increases in severity, or changes in nature during or as a consequence of the study drug phase of a human clinical trial, will also be considered an AE.
- Complications of pregnancy (e.g., spontaneous abortion, miscarriage, ectopic pregnancy, fetal demise, still birth, congenital anomaly of fetus/newborn); see [Section 7.1.11](#) for additional information.
- AEs that occur from the study screening visit onwards and throughout the duration of the study, including the follow-up off study drug period will be recorded as an AE.
- Conditions that lead to a medical or surgical procedure.

AEs do not include the following:

- Medical or surgical procedures (e.g., surgery, endoscopy, tooth extraction, transfusion) performed as a result of an AE.
- Pre-existing diseases or conditions or laboratory abnormalities present or detected before the screening visit that **do not worsen**.
- Situations where an untoward medical occurrence has not occurred (e.g., hospitalization for elective surgery, social and/or convenience admissions).
- Overdose without clinical sequelae.
- Any medical condition or clinically significant laboratory abnormality with an onset date before the informed consent form is signed is not an AE. It is considered to be pre-existing and will be documented on the medical history CRF.
- Uncomplicated pregnancy.
- An induced elective abortion to terminate a pregnancy without medical reason.

### 7.1.2 SERIOUS ADVERSE EVENTS

A serious adverse event (SAE) is any AE that meets one of the following conditions:

- Death during the period of surveillance defined by the protocol;
- Is immediately life-threatening (e.g., subject was, in the view of the Investigator, at immediate risk of death from the event as it occurred). This does not include an AE that, had it occurred in a more serious form, might have caused death;
- An event requiring inpatient hospitalization or prolongation of existing hospitalization during the period of protocol defined surveillance (even if the hospitalization is only a precautionary measure to allow continued observation). However, hospitalization (including hospitalization for an elective procedure) for a pre-existing condition that has not worsened, does not constitute an SAE;
- Results in persistent or significant disability/incapacity or substantial disruption of the ability to conduct normal life functions;
- Results in congenital anomaly or birth defect;
- An important medical event that may not result in death, be life threatening, or require hospitalization, but based upon appropriate medical judgment, may jeopardize the subject and may require medical or surgical intervention to prevent one of the outcomes listed above. Examples of such medical events include 1) allergic bronchospasm requiring intensive treatment in an emergency room or at home, 2) blood dyscrasias or convulsions that do not result in inpatient hospitalization, 3) the development of drug dependency or drug abuse or 4) the development of a malignancy;

### 7.1.3 CLARIFICATION OF SERIOUS ADVERSE EVENTS

- Death is an outcome of an AE, and not an adverse event in itself.
- The subject may not have been on investigational medicinal product at the occurrence of the event.
- Dosing may have been given as treatment cycles or interrupted temporarily before the onset of the SAE, but may have contributed to the event.
- “Life-threatening” means that the subject was at immediate risk of death from the event as it occurred. This does not include an event that might have led to death if it had occurred with greater severity.
- Complications that occur during hospitalizations are AEs. If a complication prolongs the hospitalization, it is an SAE.

- Inpatient hospitalization means that the subject has been formally admitted to a hospital for medical reasons, for any length of time. This may or may not be overnight. It does not include presentation and care within an emergency department nor does it include full day or overnight stays in observation status.

The Investigator will attempt to establish a diagnosis of the event on the basis of signs, symptoms, and/or other clinical information. In such cases, the diagnosis will be documented as the AE and/or SAE and not the individual signs/symptoms.

Serious adverse events that are ongoing should be followed until resolution or are clinically stable. The reporting period for SAEs is described in [Section 7.4.2](#).

#### **7.1.4 EVENT REPORTING FOR DISEASE PROGRESSION OR EXCLUSIONARY HISTOLOGIC FINDINGS POST-STUDY TREATMENT**

After starting study treatment, if there is histologic confirmation of progression of HSIL to microinvasive or invasive squamous cell carcinoma, the event must be reported as an SAE. For the finding of carcinoma, subjects should be managed per routine standard of care (i.e. surgical excision), discontinued from study treatment but continue on study without further biopsy. Post-study treatment histologic diagnosis of carcinoma should also be reported as an SAE. In both instances the condition for SAE reporting should be categorized as a medically important event unless another criterion is met.

#### **7.1.5 UNEXPECTED ADVERSE DRUG REACTIONS AND EXPEDITED REPORTING**

An adverse drug reaction (ADR) is any noxious and unintended responses to a medicinal product related to any dose, for which a causal relationship between a medicinal product and an adverse event is at least a reasonable possibility (i.e., there is evidence to suggest a causal relationship between the product and the adverse event). An unexpected ADR is one, the nature or severity of which is not consistent with the applicable product information (Investigator's brochure, protocol, and user manual). Reports that add significant information on specificity or severity of a known, already documented SAE constitute unexpected events. For example, an event more specific or more severe than described in the Investigator's Brochure or protocol would be considered "unexpected". Specific examples would be (a) acute renal failure as a labeled ADR with a subsequent new report of interstitial nephritis and (b) hepatitis with a first report of fulminant hepatitis.

The Sponsor will assess each serious ADR report for expectedness, to determine if it is a serious unexpected suspected adverse reaction (SUSAR) which requires prompt reporting to regulatory authorities and participating Investigators as an expedited report, according to the applicable regulatory requirements. Additional occurrences of the SUSAR will be required to be reported on an expedited basis until the applicable product information is amended.

In addition to single-case reports of SUSARs, the Sponsor shall notify regulatory authorities and participating Investigators of information that might materially influence the benefit-risk assessment of a medicinal product, sufficient to consider changes in product administration or overall conduct of a clinical investigation. Examples of such information include a clinically important increase in the rate of occurrence of a serious

expected adverse event, the identification of a significant hazard to the subject population, or a major safety finding from a study conducted in animals.

#### **7.1.6 UNANTICIPATED (SERIOUS) ADVERSE DEVICE EFFECT (UADE)**

Unanticipated adverse device effect means any serious adverse effect on health or safety or any life-threatening problem or death caused by, or associated with, a device, if that effect, problem, or death was not previously identified in nature, severity, or degree of incidence in the investigational plan or application (including a supplementary plan or application), or any other unanticipated serious problem associated with a device that relates to the rights, safety, or welfare of subjects.

Per the definition above, a UADE is a type of serious adverse event (SAE) that requires expedited reporting on the part of the sponsor. As a reminder, all SAEs regardless of relationship to device, drug or procedure are to be reported to Sponsor by the study Investigator within 24 hours. Sponsor will assess each device related SAE to determine if anticipated based on prior identification within the investigational plan.

#### **7.1.7 ASSESSING SEVERITY (INTENSITY)**

Adverse events should be captured once on the CRF at the maximum severity reported. The Investigator will grade laboratory AEs and clinical AEs with respect to the following levels of severity as per Common Toxicity Criteria for Adverse Events (CTCAE) v 4.03 for applicable subject populations:

- Mild (Grade 1)
- Moderate (Grade 2)
- Severe (Grade 3)
- Potentially Life Threatening (Grade 4)
- Death (Grade 5)

The Investigator will grade injection site reactions in accordance with September 2007 FDA Guidance for Industry—Toxicity Grading Scale for Healthy Adult and Adolescent Volunteers Enrolled in Preventive Vaccine Clinical Trials.

#### **7.1.8 CASUAL RELATIONSHIP OF CLINICAL MATERIAL TO ADVERSE EVENTS**

A causally related AE is one judged to have a reasonable possibility of a relationship to the administration of the IP and/or the investigational device. An AE may also be assessed as not related to the IP and/or the investigational device. Because the Investigator is knowledgeable about the subject (e.g., medical history, concomitant medications), administers the IP, and monitors the subject's response to the IP, the Investigator is responsible for reporting adverse events and judging the relationship between the administration of the IP and device and a subsequent AE. The Investigator is aware of the subject's clinical state and thus may be sensitive to distinctions between events due to the underlying disease process versus events that may be product related and may have observed the event. The Sponsor will assess the overall safety of the IP delivered by EP and determine whether to report expeditiously to the regulatory agencies.

Investigators should use their knowledge of the subject, the circumstances surrounding the event, available site and non-site laboratory and clinical records, and an evaluation of any potential alternative causes to determine whether or not an adverse event is considered to be related to the IP and/or the investigational device indicating "yes" or "no" accordingly. Causality should be assessed by the Investigator as "yes, related" or "no, unrelated" by the following criteria:

- Yes – there is a reasonable possibility that administration of the Study Treatment contributed to the event;
- No – there is no reasonable possibility that administration of the Study Treatment contributed to the event and there are more likely causes.

The following guidance should also be taken into consideration:

- Temporal relationship of event to administration of IP and/or the investigational device;
- Course of the event, considering especially the effects of dose reduction, discontinuation of IP, or reintroduction of IP (where applicable);
- Known association of the event with the IP, EP or with similar treatments;
- Known association of the event with the disease under study;
- Presence of risk factors in the Study Subject or use of concomitant medications known to increase the occurrence of the event

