### 1.1.11 IMIQUIMOD CREAM, 5%

Imiquimod Cream, 5% is a licensed product intended to be used in this study concomitantly with the investigational product and device. Imiquimod Cream, 5% will be centrally sourced, supplied in single-use packets (24 per box), each of which contains 250 mg of the cream, equivalent to 12.5 mg of imiquimod. The product manufacturer is Perrigo, Yeruham 80500, Israel.

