## 5. STUDY TREATMENT

### 5.1 INVESTIGATIONAL PRODUCTS

The VGX-3100 drug product contains DNA plasmids for expression of HPV-16 E6/E7 (pGX3001) and HPV-18 E6/E7 (pGX3002) antigens that have been designed and constructed using proprietary synthetic consensus DNA (SynCon™) technology. The VGX-3100 formulation to be used in this study is described in [Table 9](#) and will be presented in a clear glass vial for intramuscular injection.

Imiquimod 5% is a topical cream for external use and is supplied in single-use packets containing 250 mg of cream. Each gram of the 5% cream contains 50 mg of imiquimod in an off-white oil-in-water vanishing cream base. Inactive ingredients include benzyl alcohol, cetyl alcohol, glycerin, methylparaben, oleic acid, oleyl alcohol, polysorbate 60, propylparaben, purified water, stearyl alcohol, sorbitan monostearate, white petrolatum, and xanthan gum. There are 24 single-use packets of imiquimod in one box. The product manufacturer is Perrigo, Yeruham 80500, Israel.

Imiquimod is indicated for the treatment of external genital and perianal warts/condyloma acuminata in patients 12 year old or older. Although it is not approved by the US Food and Drug Administration for the treatment of vulvar HSIL, imiquimod is currently recommended as a non-surgical, off-label treatment option for vulvar dysplasia by the American College of Obstetricians and Gynecologists (ACOG).

VGX-3100 and imiquimod will be provided by Inovio Pharmaceuticals, Inc. or its designee.

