**Table 9. Investigational Products**

Product	Formulation	Dose
VGX-3100	6 mg (1:1 mix of SynCon™ HPV-16 E6/E7 and HPV-18 E6/E7 plasmids) in 150 mM sodium chloride and 15 mM sodium citrate	1 mL
Imiquimod Cream, 5%	12.5 mg imiquimod per 250 mg single-use packet	250 mg

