## 6.2 DURING TREATMENT PROCEDURES BY VISIT

Once eligibility has been confirmed, the subject will be randomized to receive study treatment. Visit dates and windows must be calculated from Day 0.

### 6.2.1 DAY 0

The following evaluations will be performed on Day 0 **prior to study treatment**:

- Determination of eligibility per Inclusion/Exclusion Criteria
- Review of concomitant medications and adverse events

- Randomization
- Patient Reported Outcomes
- Targeted physical assessment
- Vital signs
- Urine pregnancy test
- Whole blood and serum for immunologic assay including miRNA profile
- Cervical colposcopy
  - Photographs during colposcopic examinations of the vagina and/or cervical areas should be obtained if lesions are identified.
- Cervical cytology and ThinPrep® for cervical HPV type
  - Collect menstrual cycle status and recent gynecologic history
- OP rinse, vulvar, vaginal and intra-anal swabs
- Vulvoscopy
- Vulvar lesion photography of the qualifying lesion(s)

Study treatment will be administered and the following evaluations will be performed on Day 0 **after study treatment**:

- Post treatment AEs including injection site reaction assessment within 30-45 minutes after study treatment
- Distribute Participant Diary (PD)
- Distribute 1 box of imiquimod and the imiquimod dosing log (for subjects in the imiquimod arm)

Download EP data from device

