### 7.1.8 CASUAL RELATIONSHIP OF CLINICAL MATERIAL TO ADVERSE EVENTS

A causally related AE is one judged to have a reasonable possibility of a relationship to the administration of the IP and/or the investigational device. An AE may also be assessed as not related to the IP and/or the investigational device. Because the Investigator is knowledgeable about the subject (e.g., medical history, concomitant medications), administers the IP, and monitors the subject's response to the IP, the Investigator is responsible for reporting adverse events and judging the relationship between the administration of the IP and device and a subsequent AE. The Investigator is aware of the subject's clinical state and thus may be sensitive to distinctions between events due to the underlying disease process versus events that may be product related and may have observed the event. The Sponsor will assess the overall safety of the IP delivered by EP and determine whether to report expeditiously to the regulatory agencies.

Investigators should use their knowledge of the subject, the circumstances surrounding the event, available site and non-site laboratory and clinical records, and an evaluation of any potential alternative causes to determine whether or not an adverse event is considered to be related to the IP and/or the investigational device indicating "yes" or "no" accordingly. Causality should be assessed by the Investigator as "yes, related" or "no, unrelated" by the following criteria:

- Yes – there is a reasonable possibility that administration of the Study Treatment contributed to the event;
- No – there is no reasonable possibility that administration of the Study Treatment contributed to the event and there are more likely causes.

The following guidance should also be taken into consideration:

- Temporal relationship of event to administration of IP and/or the investigational device;
- Course of the event, considering especially the effects of dose reduction, discontinuation of IP, or reintroduction of IP (where applicable);
- Known association of the event with the IP, EP or with similar treatments;
- Known association of the event with the disease under study;
- Presence of risk factors in the Study Subject or use of concomitant medications known to increase the occurrence of the event

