### 7.3.1 ADVERSE EVENTS OF SPECIAL INTEREST

Adverse events of special interest (AESI) are the adverse events deemed related to VGX-3100 delivered with CELLECTRA™ 2000 that require expedited communication from the site to the Sponsor and meet any of the following criteria:

- Grade 3 or greater persistent administration site erythema, and/or induration recorded  $\geq 2$  hours immediately after Study Treatment
- Grade 4 or greater persistent administration site pain, tenderness recorded  $\geq 2$  hours immediately after Study Treatment
- Grade 3 or greater fever
- Grade 3 or greater systemic symptoms, including generalized pruritus

As per the Toxicity Grade for Healthy Adults. The most severe grade for that particular event is to be documented in the CRFs.

Sites will inform the Sponsor of an AESI within 24 hours via method described in [Section 7.4.2](#), to discuss whether further dosing should continue.

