### **8.11 SAFETY ANALYSES**

All AEs will be summarized among the safety population by frequency per treatment arm. These frequencies will be presented overall and separately by dose, and will depict overall, by system organ class and by preferred term, the percentage of subjects affected. Additional frequencies will be presented with respect to maximum severity and to strongest relationship to Study Treatment. Multiple occurrences of the same AE will be counted only once following a worst-case approach with respect to severity and relationship to Study Treatment. All serious AEs will also be summarized as above.

The main summary of safety data will be based on events occurring within 14 days of any dose. For this summary, the frequency of preferred term events will be summarized with percentages and exact Clopper-Pearson 95% confidence intervals. Separate summaries will be based on events occurring within 7 days of any dose and regardless of when they occurred.

Any AEs with a missing or partial onset date will be included in the overall AEs, but not be included within specified day-range summaries. AE duration will be calculated as (Stop Date – Start Date) + 1.

Measurements for vital signs as well as changes from baseline will be summarized with descriptive statistics: mean standard deviation, minimum, median, and maximum values by time point and treatment arm, for the mITT population. Baseline is defined as the last measurement prior to the first treatment administration.

The percentage of subjects with abnormal physical examination findings at each time point will be summarized by treatment study group and by body system, for the mITT population.

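### The single causality answer in section 7.1.8 rests on terms that the protocol uses both with and without imiquimod, so application-site reactions in the combination arm can be coded either way

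*Protocol*

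**What the plan says.** Section 7.1.8 (version 5.0; earlier protocol versions in the same document carry the same wording) tells investigators to "determine whether or not an adverse event is considered to be related to the IP and/or the investigational device" and to answer yes or no. The criterion for yes is that "there is a reasonable possibility that administration of the Study Treatment contributed to the event". The question is thus put in terms of IP and device, and the test in terms of Study Treatment.

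On whether imiquimod belongs to these terms, the protocol speaks both ways.

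- **Inside.** Section 5 is headed Study Treatment, and 5.1, Investigational Products, describes the cream and closes with "VGX-3100 and imiquimod will be provided by Inovio Pharmaceuticals, Inc. or its designee". Table 9 gives it a row as an investigational product: "12.5 mg imiquimod per 250 mg single-use packet".
- **Outside.** Section 1.1.11 states: "Imiquimod Cream, 5% is a licensed product intended to be used in this study concomitantly with the investigational product and device". Section 1.1.9 treats VGX-3100 and the device together as the investigational product. Section 7.1.8 itself speaks of an IP that the investigator administers and that is delivered by electroporation.
- **Study treatment as the injection alone.** Section 6.4 sets distances from tattoos and scars for study treatment plus EP, and 6.6 has the injection site inspected before and after each study treatment.

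The answer feeds section 8.11: "Additional frequencies will be presented with respect to maximum severity and to strongest relationship to Study Treatment". It also feeds the rule in 7.3.2 that pauses the study for an SAE, potentially life-threatening AE or death verified as related to Study Treatment, and the rule in 4.3.1 on Grade 4 toxicity attributable to study treatment.

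**The concern.** Section 1.1.16 names local skin and application-site reactions as the most frequent adverse reactions to the cream, so the combination arm can be expected to produce events whose obvious cause is imiquimod. Whether these count as related depends on what the reader takes IP and Study Treatment to mean, and the protocol supplies grounds for both readings. Two sites can code the same vulvar reaction differently while each follows the text.

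A second difficulty remains even if all sites agree to include imiquimod. For a systemic event that either product could cause, one combined yes does not say which product the investigator had in mind, and no later analysis can recover it. At stake is whether the related-AE figures of the combination arm can be interpreted, and whether rules keyed to relatedness work the same way at every site.

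**Working it through.** The protocol states no figure on this point, so the check is mainly a comparison of passages.

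**Step 1: one event under two readings.** Take a vulvar erosion at the application site in a woman whose injections go into the deltoid or quadriceps.

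- A site that follows Table 9 and the heading of section 5 treats imiquimod as IP and Study Treatment. The cream plausibly contributed, so the answer is yes.
- A site that follows 1.1.11 and the IP delivered by EP in 7.1.8 treats imiquimod as something used alongside. The causality guidance in 7.1.8 tells investigators to weigh concomitant medications known to increase the event. Imiquimod is then the more likely cause, and the answer is no.

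**Step 2: strength of each side.** For IP the conflict is explicit (Table 9 against 1.1.11). For Study Treatment it is weaker: inclusion comes from a section heading, exclusion from usage in 6.4 and 6.6, and the protocol text shown has no definition. The Day 0 list in 6.2.1 ("Study treatment will be administered and the following evaluations will be performed on Day 0", with the imiquimod box handed out afterwards) adds little, because it may reflect visit order only.

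**Step 3: size.** Inputs: 12 women planned for the arm (section 3). The number k of these women with an application-site reaction is not given, so it is assumed and varied.

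- Inclusive reading: related percentage = k/12.
- Narrow reading: related percentage = 0/12 = 0%.
- One woman recoded: 1/12 = 8.3 percentage points.

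| Assumed k | Inclusive | Narrow |
|---|---|---|
| 1 | 8.3% | 0% |
| 3 | 25% | 0% |
| 6 | 50% | 0% |
| 9 | 75% | 0% |

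If sites differ, the reported figure falls between the columns. Because enrollment was halted, the arm may be smaller than 12 and the step per woman larger.

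**Step 4: what depends on the answer in version 5.0.**

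| Item | Exposed? |
|---|---|
| 8.11 frequencies by relationship | Yes |
| 7.3.2 related SAE, life-threatening AE or death | Yes |
| 4.3.1 Grade 4 discontinuation | Yes |
| 8.11 all-AE summaries | No; they count events regardless of relationship |
| 7.3.1 AESI definition and its one-third rule | No; the definition names its own attribution |
| 7.3.2 rules on three same Grade 3/4 events or two identical Grade 4 toxicities | Little for known imiquimod reactions; events must be unexpected and verified |

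**Step 5: timing.** Version 3.0 is dated 26 March 2019 and version 5.0 is dated 19 December 2019: 268 days, and 268/7 = 38.3 weeks. Imiquimod is applied for 20 weeks. If enrollment to the arm stopped within 38.3 − 20 = 18.3 weeks of the version 3.0 date, all imiquimod use had ended by version 5.0. The remaining issue is then mostly how events already recorded are attributed.

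**The case against.** The strongest reply is that little turns on this. Secondary endpoint 1b is all adverse events; the main safety summary in 8.11 counts events within 14 days of any dose whatever their cause; the arms are shown separately; and a vulvar reaction is distinguishable by site from one at the deltoid or quadriceps. All of that stands, and it confines the problem to the relationship table and the two rules in 7.3.2 and 4.3.1.

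Second, the case report form is not shown. Section 7.1.1 says that it records relationship to investigational products, with an optional plural, so product-level fields may already exist. That is possible, but 7.1.8 does not ask for them, and the plural does not settle whether imiquimod is one of the products.

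Third, table layout is normally left to the SAP. That is true of layout, but a SAP cannot split a combined answer that was never recorded by component.

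A reader might infer that AESI and UADE reporting are compromised too. The documents do not support this. Section 7.3.1 states its own attribution ("Adverse events of special interest (AESI) are the adverse events deemed related to VGX-3100 delivered with CELLECTRA™ 2000"), and 7.1.6 gives the sponsor a separate assessment of device-related SAEs. Nor do they support the inference that known imiquimod reactions would readily trigger the three-subject Grade 3/4 pause: version 5.0 reworded all four pausing rules and limits that one to unexpected events, while 1.1.16 lists the cream's application-site reactions as already reported.

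**Conclusion.** The point holds in a limited form. Section 7.1.8 asks for one answer in terms that the protocol uses both with and without imiquimod, so an application-site reaction in the combination arm can be coded related or unrelated with textual support either way. The related percentage for those reactions is uncertain between 0% and their full incidence, at 8.3 percentage points per woman if the arm has its planned 12. The documents give no incidence, so the actual error cannot be stated.

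It would go too far to infer that every adverse event in the arm is either related or unrelated as a block. A systemic event that VGX-3100 could plausibly have caused is related under both readings. For those events the loss is that the product responsible cannot be identified.

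The conclusion assumes that the form follows 7.1.8 and holds a single answer. If it already records each product separately, only the wording conflict remains. With a small closed arm and the all-AE summaries intact, this is a cheap improvement worth making, not a threat to the trial's main results.

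**What to change.** 1. Define IP and Study Treatment once, stating whether each includes imiquimod, and bring section 5, Table 9, 1.1.9, 1.1.11, 6.4, 6.6 and 7.1.8 into line.
2. In 7.1.8, replace the combined answer with separate yes/no answers for VGX-3100, the EP device and imiquimod (the last for the combination arm only).
3. In 8.11, show related AEs by component for the combination arm.
4. Reconcile 4.3.1, 7.1.8 and 7.3.2 so that they use the same stated attribution. Which attribution should govern pausing or discontinuation is a clinical decision for the sponsor; the need is that the passages agree.
5. For events already recorded in the combination arm, query the sites for attribution by component.

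The cost is wording, up to two extra CRF fields (three answers in place of one, fewer if the form already separates products), and attribution queries for about 12 women. Answers given retrospectively will be less reliable than contemporaneous ones, and the report should mark them as such.
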